7.6.4. Electrocardiograms

All 12-lead ECGs will be performed at the study site with the subject in a recumbent or semirecumbent position after 5 minutes of rest.

The 12-lead ECG readings will be interpreted by the investigator at the site to be used for immediate subject management. The decision to include or exclude a subject or withdraw a subject from the study treatment based on an ECG flagged as "Abnormal, Clinically Significant" is the responsibility of the investigator, in consultation with the medical monitor, as appropriate. Clinically notable abnormalities that are considered clinically significant in the judgment of the investigator are to be reported as AEs. In the event that a single QTc is > 470 milliseconds at screening, the subject may enroll if the average QTc for the 3 ECGs is < 470 milliseconds or with approval from the medical monitor. For subjects with an intraventricular conduction delay (QRS interval > 120 milliseconds) at screening, the JTc interval may be used in place of the QTc with medical monitor approval. In addition, the JTc interval should be used for all subsequent assessments.

7.6.5. Laboratory Assessments

A certified laboratory local to the study site and subject will perform all clinical laboratory assessments for safety (ie, blood chemistries, hematology assessments, coagulation tests, endocrine function, and urinalysis). The investigative site will enter the laboratory results and laboratory normal ranges into the eCRF. All local laboratory assessments should be performed using standard procedures on the days indicated in [Table 13](#). [Table 14](#) lists the specific laboratory analytes required for each test. Additional testing may be required by the sponsor based on emerging safety data. Additional tests may also be performed if clinically indicated.

Screening laboratory assessments must be performed within 7 days of Cycle 1 Day 1. If performed more than 7 days before Cycle 1 Day 1, then the tests must be repeated and eligibility confirmed before study drug administration on Cycle 1 Day 1. Laboratory samples collected on study Day 1 must be performed before study drug administration. After Cycle 1, predose laboratory procedures can be conducted up to 72 hours before study drug administration (within the 3-day study window), and results should be reviewed by the investigator or qualified designee and found to be acceptable before a new cycle of treatment is initiated.

7.6.5.1. Pregnancy Testing

A local laboratory serum pregnancy test will be required for all women of childbearing potential during screening and at EOT. The serum pregnancy test performed at screening must be performed within 72 hours before the first dose of study drug. Urine pregnancy tests will be performed locally as outlined in [Table 13](#), as medically indicated, or per country-specific requirement. If a urine pregnancy test is positive, then the results should be confirmed with a serum pregnancy test.

If the serum pregnancy test is negative after a urine test was positive, then the investigator will assess the potential benefit/risk to the subject and determine whether it is in the subject's best interest to resume study treatment and continue participation in the study.

7.6.5.2. Hepatitis Screening Tests

Hepatitis screening assessments will be performed at the screening visit ([Table 13](#)) to rule out hepatitis infection; required analytes are shown in [Table 14](#). Generally, hepatitis tests should be performed early in the screening process due to the length of time needed to obtain the results. Additional tests may be performed if clinically indicated.

7.7. Efficacy Assessments

7.7.1. Modified RECIST Assessment Disease

Modified RECIST will be applied by the site as a basis for Protocol guidelines related to disease status (eg, discontinuation of study therapy). As noted in Section [1.5.4.1](#), RECIST v1.1 has been adapted to account for the unique tumor responses seen with immunotherapy ([Wolchok et al 2009](#)).

If radiologic imaging shows progressive disease, tumor assessment may be repeated at a minimum of 4 weeks, but no later than 6 weeks later to confirm progression, with the option of continuing treatment while awaiting radiologic confirmation of progression. [Table 15](#) provides instructions on how to proceed with treatment based on the subject's clinical status once the initial scan showing radiologic evidence of progression is observed.

Subjects may receive treatment while waiting for confirmation of progression if they are clinically stable as defined by the following criteria:

- Absence of clinically significant signs and symptoms (including worsening of laboratory values) indicating disease progression.
- No decline in ECOG performance status.
- Absence of rapid progression of disease.
- Absence of progressive tumor at critical anatomical sites (eg, cord compression) requiring urgent alternative medical intervention.

Table 15: Imaging and Treatment After First Radiologic Evidence of Progressive Disease

	Clinically Stable		Clinically Unstable	
	Tumor Imaging	Treatment	Tumor Imaging	Treatment
First radiologic evidence of progression	Repeat imaging 4-6 weeks to confirm progression	May continue study treatment at the investigator's discretion while awaiting confirmatory tumor imaging	Repeat tumor imaging 4-6 weeks to confirm progression per physician discretion only	Discontinue treatment
Repeat scan confirms progression	No additional tumor imaging required	Discontinue treatment	No additional tumor imaging required	N/A
Repeat scan shows SD, PR, or CR	Continue regularly scheduled tumor imaging assessments	Continue study treatment at the investigator's discretion	Continue regularly scheduled tumor imaging assessments	May restart study treatment if condition has improved and/or clinically stable per investigator's discretion

As noted above, if disease progression is observed, the study site may elect to continue treatment, repeat imaging at a minimum of 4 weeks, but no later than 6 weeks later, and assess tumor response or confirmed progression per mRECIST.

In determining whether or not the tumor burden has increased or decreased, study site investigators should consider all target lesions as well as nontarget lesions. Subjects who are deemed clinically unstable are not required to have repeat tumor imaging for confirmation. If radiologic progression is confirmed by subsequent scan, then the subject should be discontinued from study treatment. If radiologic progression is not confirmed, then the subject should resume or continue study treatment and have the next tumor imaging according to the Protocol schedule (see [Table 12](#)). If progression is not confirmed and the subject continues on treatment, then the next scan that documents disease progression (and is confirmed by a second scan at least 4 weeks, but no later than 6 weeks later) will be considered the date of disease progression.

If a subject has confirmed radiographic progression (ie, 2 scans at least 4 weeks, but no later than 6 weeks, apart demonstrating progression) per mRECIST, but the subject is achieving a clinically meaningful benefit, an exception to continue treatment may be considered after consultation with the medical monitor. Clinically stable subjects at the confirmatory scan should also have no further increase in the target lesions, no unequivocal increase in nontarget lesions, and no additional new lesions develop (nonworsening disease progression) to continue study treatment.

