2.2.2. Secondary Endpoints

- ORR, defined as the percentage of subjects having CR or PR, will be determined by investigator assessment of radiographic disease assessments per RECIST v1.1.
- DOR, defined as the time from the earliest date of disease response (CR or PR) until earliest date of disease progression or death due to any cause, if occurring sooner than progression, will be determined by investigator assessment of radiographic disease assessments per RECIST v1.1.
- DCR, defined as the percentage of subjects having CR, PR, or SD, will be determined by investigator assessment of a radiographic disease assessments per RECIST v1.1.
- Duration of disease control (CR, PR, and SD) as measured from first report of SD or better until disease progression or death from any cause, if occurring sooner than progression, will be determined by investigator assessment of radiographic disease per RECIST v1.1.
- PFS, defined as the time from the start of combination therapy until the earliest date of disease progression or death due to any cause, if occurring sooner than progression, as determined by investigator assessment of objective radiographic disease assessments per RECIST v1.1.
- Safety and tolerability will be assessed by monitoring frequency, duration, and severity of AEs.

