5.5. Withdrawal of Subjects From Study Treatment

5.5.1. Withdrawal Criteria

A subject may choose to withdraw from the study treatment at any time or be withdrawn from the study treatment by the investigator or sponsor, if the subject is noncompliant with the study requirements. If a subject is withdrawn from study treatment, then every reasonable effort should be made to determine the reason for withdrawal, and this information should be recorded in the eCRF.

Subjects **must** be withdrawn from **study treatment** for the following reasons:

- The subject becomes pregnant.
- Consent is withdrawn. Subjects may choose to withdraw from the study at any time without penalty of jeopardizing their health care or loss of benefits to which the subject is otherwise entitled.
Note: Consent withdrawn means that the subject can no longer be followed and no additional data can be collected. Subjects may choose to discontinue study treatment and remain in the study to be followed for safety through the safety follow-up period.
- Further participation would be injurious to the subject's health or well-being, in the investigator's medical judgment.
- Unacceptable toxicity (see Section 5.4.9). Subjects with unacceptable toxicities must be withdrawn from study treatment but will continue in the follow-up phase of the study (see Section 6.4).
- The study is terminated by the sponsor.
- The study is terminated by the local health authority, IRB, or IEC.
- The subject has received 24 months of treatment with study drug.

A subject **may** be discontinued from **study treatment** as follows:

- Confirmed radiographic progression of disease per RECIST v1.1 (see Section 7.7.1). A subject may be granted an exception to continue on treatment with confirmed radiographic progression if clinically stable or clinically improved (see Section 7.7.1). **Note:** For unconfirmed progression, see Section 7.7.1.
- If, during the course of the study, a subject is found not to have met eligibility criteria (see Section 3), the medical monitor, in collaboration with the investigator, will determine whether the subject should be withdrawn from the study.
- If a subject is lost-to-follow-up or noncompliant with study procedures or study treatment in the investigator's opinion, the sponsor should be consulted for instruction on handling the subject.

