7.7.1.1.2. Tumor Imaging During the Study

The first imaging assessment should be performed 8 weeks after the first dose of INCAGN01949 and then every 8 weeks (56 days \pm 7 days) for 12 months (until the Week 56 scan) and then every 12 weeks thereafter until disease progression is determined. Imaging assessments may be done more frequently if clinically indicated. **Imaging should not be delayed for delays in cycle starts.**

Per mRECIST, response may be confirmed by a repeat radiographic assessment not less than 4 weeks from the date the response was first documented. The scan for confirmation of response may be performed at the earliest 4 weeks after the first indication of response or at the next scheduled scan, whichever is clinically indicated.

Imaging should continue to be performed until documented disease progression, the start of new anticancer treatment, withdrawal of consent, death, or the end of the study, whichever occurs first. Disease progression may be confirmed at least 4 weeks, but no later than 6 weeks, after the first scan indicating progression in clinically stable subjects. Subjects who have unconfirmed disease progression may continue on treatment until progression is confirmed, provided that they have met the conditions detailed in Section 7.7.1. A central imaging vendor will not be used in this study.

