7.3.7.1. Progression-Free Survival by RECIST v1.1

Under RECIST v1.1, PFS is defined as the length of time between the baseline visit (Day 1) and the earlier of death or first assessment of PD as assessed by RECIST v1.1.

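### Unconfirmed first progression: Protocol 7.7.1 dates the event at a later confirmed scan, and SAP 7.3.4 carries the same mRECIST rule into the RECIST v1.1 analysis of duration of disease control

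*Protocol*

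**What the plan says.** **Protocol 7.7.1** (within 7.7, Efficacy Assessments) allows a repeat scan after a first PD: "tumor assessment may be repeated at a minimum of 4 weeks, but no later than 6 weeks later to confirm progression". If PD is not confirmed, the subject continues or resumes treatment and should "have the next tumor imaging according to the Protocol schedule". The dating rule follows. It opens "If progression is not confirmed and the subject continues on treatment, then the next scan that documents disease progression", requires that scan to be confirmed in turn, and closes "but no later than 6 weeks later) will be considered the date of disease progression". The sentence names no response criterion and no purpose.

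**Protocol 5.5.1** lists as a reason for which treatment may be stopped: "Confirmed radiographic progression of disease per RECIST v1.1". For the detail it refers to 7.7.1, the mRECIST section.

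**Protocol 1.5.4.1.1** says that Amendment 3 removed mRECIST as an endpoint and that its principles may still guide decisions to stop treatment.

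**Protocol 2.2.2** defines the endpoints by investigator assessment per RECIST v1.1. PFS runs "until the earliest date of disease progression or death due to any cause", and DOR also ends at the earliest progression or death. Duration of disease control ends at progression or death, without the word *earliest*.

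**SAP 7.3.7.1** ends RECIST v1.1 PFS at "the earlier of death or first assessment of PD as assessed by RECIST v1.1". SAP 7.3.3.1 does the same for DOR. Table 7 dates PFS progression at the first overall response of PD, and DOR censoring follows that table.

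**SAP 7.3.4** defines duration of disease control for RECIST v1.1 and mRECIST together. For the assessment of PD it refers to 7.3.2.3, which is the mRECIST section. Table 6 there disregards a PD that is followed within 4 to 6 weeks by CR, PR, SD or a non-evaluable scan.

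**The concern.** With mRECIST gone as an endpoint, each time-to-event endpoint should have one progression date, set by RECIST v1.1. Two pieces of text can still bring in a second date that depends on confirmation.

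The first is the dating sentence in 7.7.1. A decision to stop treatment needs no assigned event date, so a sentence that assigns one can be taken for an endpoint rule. The label in 5.5.1 makes that more likely. The investigator is the assessor, and there is no central imaging vendor (Protocol 7.7.1.1.2).

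The second is more serious because it lies in the analysis rules. For duration of disease control the SAP sends the RECIST v1.1 analysis to the mRECIST confirmation table, and Protocol 2.2.2 does not correct this. Two programmers could produce different Kaplan-Meier estimates from the same scans, and the confirmation-based estimate would be the longer wherever the two differ.

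**Working it through.** **Step 1. Which rule governs each endpoint under RECIST v1.1**

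| Endpoint | Protocol 2.2.2 | SAP | Does confirmation enter? |
|---|---|---|---|
| PFS | earliest progression or death | first PD (7.3.7.1, Table 7) | No |
| DOR | earliest progression or death | first PD (7.3.3.1; censoring as Table 7) | No |
| Duration of disease control | progression or death, *earliest* absent | PD criteria of 7.3.2.3 (7.3.4) | Yes, as written |

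SAP 7.3.3.2 has the same pointer to 7.3.2.3, but that subsection concerns DOR by mRECIST only. Section 7.3.4 has no such split, so its pointer covers both criteria.

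**Step 2. When a date moves**

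The 7.7.1 sentence applies only if the first PD is not confirmed and treatment continues. If the first PD is confirmed, the sentence moves no date. Table 6 is similarly limited: it lets a PD stand if a second PD follows, or if treatment or study ends or new anticancer therapy starts in the window.

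**Step 3. How far it moves**

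Inputs:
- Scan interval to Week 56: 8 weeks, or 56 days. Protocol 7.7.1.1.2: "The first imaging assessment should be performed 8 weeks after the first dose of INCAGN01949 and then every 8 weeks".
- Scan interval after Week 56: 12 weeks, or 84 days (same section).
- Scan window: 7 days either side (Protocol Table 12, footnote j).
- Repeat scan: 28 to 42 days after the first PD (Protocol 7.7.1).
- Unscheduled scans are allowed (Protocol 7.7.1.1.2).

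The documents state no figure for the shift, so there is none to reproduce. The one related figure checks: SAP 7.3.2.2 gives the minimum SD interval as 56 − 7 = 49 days.

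Shift = date of the later PD scan − date of the first RECIST v1.1 PD. If the later PD is at the next scheduled scan:
- First PD at a scheduled scan up to Week 48: nominal 56 days (8 weeks). Shortest 56 − 7 − 7 = 42 days (6 weeks); longest 56 + 7 + 7 = 70 days (10 weeks).
- First PD at Week 56 or later: nominal 84 days (12 weeks). Shortest 84 − 14 = 70 days (10 weeks); longest 84 + 14 = 98 days (14 weeks).
- First PD on an unscheduled scan: repeat scan at 28 days and the next scan at least 1 day later, so 28 + 1 = 29 days (about 4 weeks) at the shortest.
- If the later PD comes at a subsequent scan, each extra interval adds nominally 8 or 12 weeks.

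**Step 4. Example for duration of disease control**

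Take SD at Week 8, first PD at Week 16, SD on the repeat scan at Weeks 20 to 22, and PD at Week 24 confirmed at Weeks 28 to 30.
- First RECIST v1.1 PD: 16 − 8 = 8 weeks of disease control.
- Table 6 as referenced by SAP 7.3.4: 24 − 8 = 16 weeks.

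The same scans give 8 or 16 weeks. A subject with PD at the Week 8 scan and nothing better before it has no RECIST v1.1 disease control to measure. For that subject only the recorded PFS date could differ.

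**The case against.** The strongest reply is scope. Section 7.7.1 is headed Modified RECIST, its opening sentence ties it to site guidance on disease status such as stopping therapy, and 1.5.4.1.1 confines mRECIST to treatment decisions. On that reading, two dates under two criteria are not two event dates for one endpoint. The SAP supports this for PFS and DOR: it defines each criterion separately, and by its Section 2.1 it stays effective under later amendments. It also categorises the RECIST v1.1 overall response at every assessment (7.3.1), and the documents describe no investigator-entered progression date that feeds the endpoints.

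For the analysis of PFS and DOR this reply stands. A reader might infer from 7.7.1 that these endpoints have two competing dates in the analysis. The SAP does not support that; what remains is the risk that sites record the date differently.

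A reader might also infer that a response or SD after the first PD would count. SAP 7.3.2.1 rules this out for confirmed best response, and 7.3.2.2 takes unconfirmed best response only up to the first PD.

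The reply does not reach duration of disease control, where the SAP itself directs the RECIST v1.1 analysis to mRECIST rules. Nor does it explain why 5.5.1 attributes confirmed progression under 7.7.1 to RECIST v1.1.

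**Conclusion.** The point holds in two parts of unequal weight.

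- **Duration of disease control:** the SAP rule is wrong or at best ambiguous for the RECIST v1.1 analysis. As written, an unconfirmed first PD can be ignored.
- **PFS and DOR:** the analysis rules are clear. The unrestricted sentence in 7.7.1 and the label in 5.5.1 leave only a risk of inconsistent site recording.

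The sizes in Step 3 apply to a subject whose first PD is unconfirmed, who continues treatment and who later has a confirmed PD. Eight weeks is the nominal shift and should not be read as a minimum. It would also be wrong to infer that every confirmed progression is redated.

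The documents do not say how many of the 52 enrolled subjects meet these conditions, and I make no estimate. For duration of disease control a subject must also have had SD or better before the first PD.

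The consequence is limited. Only Phase 1 analyses will be done (Protocol 9), these are secondary endpoints, and no formal tests are planned (Protocol 9.3). No sample size or error rate depends on this point.

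**What to change.** 1. **Protocol 7.7.1:** state that the dating sentence applies to mRECIST only and sets no endpoint date.
2. **Protocol 2.2.2 and SAP 7.3.3, 7.3.4 and 7.3.7:** state that PFS, DOR and duration of disease control all use the first RECIST v1.1 PD, taken from the per-visit overall response, whether or not it is later confirmed. Add *earliest* to the Protocol definition of duration of disease control.
3. **SAP 7.3.4:** restrict the reference to 7.3.2.3 to mRECIST, or remove it. The SAP is dated 06 FEB 2018, is based on Amendment 1 and still lists mRECIST endpoints, so one revision can cover both matters.
4. **Protocol 5.5.1 and 7.7.1:** reconcile the criterion named in each. Which criterion should govern stopping treatment is for the sponsor to settle; this point takes no position.

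The cost is a few sentences in a Protocol amendment or clarification letter and in a SAP revision. No new data are needed, since the SAP already plans a listing of overall response assessments (Appendix A, Listing 2.5.3).

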7.7.1.1. Tumor Imaging

The same imaging technique should be used in a subject throughout the study. The baseline scan must be a contrast CT or MRI, except in circumstances where there is a contrast allergy or with medical monitor approval. When the CT component of a positron emission tomography/CT uses higher energy and thinner slices, it may be acceptable with medical monitor approval.

Images of the chest, abdomen, and pelvis are required for all subjects. Additional imaging of anatomical sites (eg, head, neck, brain, etc) should be performed as applicable for the cancer under study.

7.7.1.1.1. Tumor Imaging During Screening

Initial tumor imaging must be performed within 28 days before the first dose of study treatment. The site study team must review prestudy images to confirm that the subject has measurable disease per RECIST v1.1. Tumor lesions that are located in a previously irradiated area or in an area subjected to other locoregional therapy should not be selected as target lesions. If a subject only has lesions in an area previously irradiated or subjected to locoregional therapy, then the subject will be allowed to enroll.

Computed tomography or MRI scan of the brain will be performed at screening if there are signs or symptoms suggesting that the subject has disease involvement in the CNS. An MRI of the brain will also be required at screening for all subjects with melanoma.

Scans performed as part of routine clinical management are acceptable for use as the screening scan if they are of diagnostic quality and performed within 28 days before the first dose of study treatment.

7.7.1.1.2. Tumor Imaging During the Study

The first imaging assessment should be performed 8 weeks after the first dose of INCAGN01949 and then every 8 weeks (56 days \pm 7 days) for 12 months (until the Week 56 scan) and then every 12 weeks thereafter until disease progression is determined. Imaging assessments may be done more frequently if clinically indicated. **Imaging should not be delayed for delays in cycle starts.**

Per mRECIST, response may be confirmed by a repeat radiographic assessment not less than 4 weeks from the date the response was first documented. The scan for confirmation of response may be performed at the earliest 4 weeks after the first indication of response or at the next scheduled scan, whichever is clinically indicated.

Imaging should continue to be performed until documented disease progression, the start of new anticancer treatment, withdrawal of consent, death, or the end of the study, whichever occurs first. Disease progression may be confirmed at least 4 weeks, but no later than 6 weeks, after the first scan indicating progression in clinically stable subjects. Subjects who have unconfirmed disease progression may continue on treatment until progression is confirmed, provided that they have met the conditions detailed in Section 7.7.1. A central imaging vendor will not be used in this study.

